Visit	-1	1	2	3	4	5	n				Q12W	During on-treatment period, after Day 29, visits
Study Day (± Visit window)	-28 to -1	1	15 (± 1)	22 (± 1)	29 (± 1)	43 (± 1)	n + 14 d (± 2)	(Within 7 days of decision to disconti nue)	30 d (± 5)	90 d (± 5)	(± 7)	will be every 2 wks on days of avelumab infusions until EoT. All participants discontinuing study interventions for any reason must undergo EoT Visit within 7 days after decision to discontinue study interventions, but (if possible) before any new antineoplastic therapy is started. The safety follow-up period will be 30 days (± 5 days) and 90 days (± 5 days) after the last dose of avelumab, see Section 4.1.1.3.
M3814		Cont	inuou	s BID	dosi	ng (7	days/wk)					See Section 6.6.5.1 for details.
Premedication (avelumab)		x	x		x	X						Required only for first 4 avelumab infusions, as needed thereafter. See Section 6.5.5.
Avelumab		x	X		x	x	x					800 mg iv Q2W until PD. For post-PD treatment, see Section 6.6.6. For post-CR treatment, see Section 4.1.1.2.
Tumor Material	x		See Notes									CCI
Survival	х	x	x	x	x	x	х	x	x	x	x	All participants will be followed up for survival and use of subsequent anticancer treatment (by phone after EoT) every 12 wks until 1 year after last participant has received the last dose of study interventions or dies, whichever comes first.

2: phone call visit.

AE=adverse event, β-HCG=beta human chorionic gonadotropin, BID=twice daily, BP=blood pressure, CT=computed tomography, ctDNA=circulating tumor DNA, d=days, ECG=electrocardiogram, ECOG=Eastern Cooperative Oncology Group, EoT=End of Treatment Visit, FSH=follicle-stimulating hormone, FU=follow-up, HIV=human immunodeficiency virus, mo=months, MRI=magnetic resonance imaging, PE=physical examination; PK=pharmacokinetic, PD=progressive disease, CCI QTCF= Fridericia's Correction Formula, QxW=every x weeks, RECIST=Response Evaluation Criteria in Solid Tumors, free T4=free thyroxine, TSH=thyroid-stimulating hormone, wk=week, WOCBP=women of childbearing potential.

Table 2 Schedule of Activities – Dose-Limiting Toxicity Evaluation Period – Part B (M3814 + Radiotherapy + Avelumab)

Study Period	Screeni ng	DLT	Evalua (M3814		eriod W + avelu		4	Notes
Study Visit	1	2	3-6	7-10	11	12	13	
Study Day (± Visit window)	-35 to -1	1	2-5 (± 1)	8-11 (± 1)	12	15 (± 1)	29 (± 1)	
M3814		x	x	X	x			M3814 QD 5 d/wk (only on days of radiation). See Section 6.6.5.2.
RT 3 Gy × 10 (5 FD/W)		x	x	х	x			RT 3 Gy/fraction, 5 FD/wk. RT to be given 1.5 h (± 30 min) after M3814.

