	Blood Volume (approximate)	CCI	8.5 mL	9 mL	CCI	2 mL	CCI	3.5 mL	CCI
Week 1 (Day 1)	Predose (approximate)	GC)	х	x	x CCI)	х	x CCI)	х	х
	1					Х			
	Eol							X	
	2					X	X		
	3					X			
	4					X	X		
	6					X	X		
Week 3 (Day 15)	predose		X	X	Х	X		X	X
	1					X			
	2					X			
	3					X			
	4					X			
	6					X			
Week 4 (Day 22)	predose					X			
	2					X			
	6					X			
Week 5 (Day 29)	predose		X	X		X		X	X
	Eol							X	
Week 9 (Day 57)	predose		X	X	Х			X	X
Week 13 (Day 85)	predose		X		Х			X	Х
Weeks 25, 37, 49	predose				Х			Х	Х

			M381	4 and Avelumab		M:	3814	Avelumab		
Week (Day)	Time (h)	CCI	Soluble Factors	lmmune phenotyping	CCI	PK	CCI	PK	CCI	
EoT for M3814 (only applies if M3814 treatment is stopped. If avelumab and M3814 treatment are stopped at the same time prior to Week 49, only 1 sample for immune phenotyping and plasma ctDNA should be collected).				х	х	х				
EoT for avelumab (if prior to Week 49)			X	x	x			x		
30-Day Safety FU (if prior to Week 49)								x	Х	

Eol=end of infusion; EoT=End of treatment, FU=follow-up,

, PK=pharmacokinetic,

Table 6 Pharmacokinetic and Biomarker Blood Sampling Schedule – Part B (M3814 + Radiotherapy + Avelumab)

	M3814 and Avelumab						814	Avelu	ımab	Notes
Week (Day)	Time (h)	CCI	Soluble Factors	Immune phenoty ping	CCI	PK	CC	PK	CCI	PK and/or Pd sampling collection times may be modified based on emerging data from prior dose levels by the SMC. M3814 PK sampling should be performed within ± 10 min for the first 2 h postdose sample collections, and within ± 20 min for subsequent sampling at each sampling day. The M3814 predose sample should be taken within 1 h before dosing at each sampling day. Avelumab PK and ADA sampling should be performed within 120 minutes prior to dose and within 15 minutes before Eol.
	Blood volume (approximate)	CCI	8.5 mL	9 mL	CCI	2 mL	CCI	3.5 mL	CCI	
Week 1 (Day 1; FD1)	Predose (approximate)		x	x	4		60			
	1					Х				Post M3814 administration.
	Eol							Х		
	2					Х	X			Post M3814 administration.
	4					Х	X			Post M3814 administration.
	6					X	X			Post M3814 administration.
Week 1 Day 2 (FD2)	Predose					x	x			For M3814 parameter calculations, the predose value will serve as an estimate for the 24 h postdose concentrations of the previous fraction day.
	2					Х				Post M3814 administration.

			M3814 and	Avelumab		М3	814	Avel	umab	Notes

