Week (Day)	Time (h)	C	Soluble Factors	Immune phenoty ping	CCI	PK	Ö	PK	O	PK and/or Pd sampling collection times may be modified based on emerging data from prior dose levels by the SMC. M3814 PK sampling should be performed within ± 10 min for the first 2 h postdose sample collections, and within ± 20 min for subsequent sampling at each sampling day. The M3814 predose sample should be taken within 1 h before dosing at each sampling day. Avelumab PK and ADA sampling should be performed within 120 minutes prior to dose and within 15 minutes before Eol.
Week 2 (Day 8; FD6)	Predose		x			x				For M3814 PK parameter calculations, the predose value will serve as an estimate for the 24 h postdose concentrations of the previous fraction day.
	2					X				post M3814 administration.
Week 2 (Day 12; FD10)	Predose		X	X	x	x	X			For M3814 PK parameter calculations, the predose value will serve as an estimate for the 24 h postdose concentrations of the previous fraction day. If Day 12 (FD10) is a Friday, PK and Pd sampling must be done on Day 11 (FD9). Following Day 12 (FD 10), avelumab predose PK should be collected prior to next infusion, every 6 wks until wk 25 and then at 12-wk intervals while on avelumab treatment.
	2					Х	X			Post M3814 administration.
	4					X	X			Post M3814 administration.
	6					X				Post M3814 administration.
Week 3 (Day 15)	predose		x	х	x			х	х	
Week 5 (Day 29)	predose		х	х				х	х	

			M3814 and	Avelumab		М3	814	Avel	umab	Notes
Week (Day)	Time (h)	CCI	Soluble Factors	Immune phenoty ping	CCI	PK	C	PK	CCI	PK and/or Pd sampling collection times may be modified based on emerging data from prior dose levels by the SMC. M3814 PK sampling should be performed within ± 10 min for the first 2 h postdose sample collections, and within ± 20 min for subsequent sampling at each sampling day. The M3814 predose sample should be taken within 1 h before dosing at each sampling day. Avelumab PK and ADA sampling should be performed within 120 minutes prior to dose and within 15 minutes before Eol.
	Eol							Х		
Week 9 (Day 57)	predose		х	х	х			х	х	
Week 13 (Day 85)	predose				х			х	х	
Week 25, 37, 49	predose				х			х	х	
EoT for M3814						Х				
EoT for avelumab			х	х	х			х		If prior to W49.
30-day Safety FU								X	X	If prior to W49.

, Eol=end of infusion, EoT=End of Treatment, F=fractions, FD=fraction day, FU=follow-up, PK=pharmacokinetics, SMC=Safety Monitoring Committee.

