Dose escalation will be based on the presence/absence of DLTs and study intervention-related clinically relevant adverse events during the DLT period. Available relevant safety data which occur during the RT Safety Follow-up at 1, 3, and 12 months. Available PK and Pd data will also be taken into consideration.

- M3814 will be administered once a day for 5 days followed by 2 days off for 10 days in total (i.e. to the same schedule as RT).
- b Radiotherapy, 30 Gy is delivered as 3 Gy per fraction per day for 5 days followed by 2 days off for 10 days in total (i.e. to the same schedule as M3814).
- c Avelumab will be administered Q2W as an IV infusion over 1 hour, starting on Day 1, at a fixed dose of 800 mg in all dose levels.
- d Dose Level -1 can be evaluated upon decision of the SMC.
- e Dose Level 1 is the starting dose.

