The total dose per selected site of 30 Gy will be given in 10 daily fractions of 3 Gy prescribed to the PTV with at least 95% of the PTV receiving 30 Gy. An acceptable variation is at least 90% of the PTV receiving 30 Gy. The maximum dose for any contiguous volume of no more than 0.03 cc inside the PTV must not exceed 120% of the prescribed dose. An acceptable deviation is a maximum dose inside the PTV of up to 125% of the prescribed dose. The minimum dose (0.03 cc) to the PTV volume should be no less than 27 Gy. All radiation doses will be calculated with inhomogeneity corrections.

Radiation Treatment Schedule

Localization, Simulation, and Immobilization for radiation treatment planning, as outlined in "Localization, Simulation, and Immobilization", will be performed no more than 35 days and no

less than 1 day before the first day of radiation treatment. The participant can initiate treatment any day of the week. Treatment will be delivered daily for 10 working days (generally Monday to Friday, with 2 days off [Saturday and Sunday]). Disruptions to the planned radiation treatment schedule should be avoided if at all possible. Any unexpected treatment break lasting > 2 days should be reported to the Investigator.

Table 21 Radiation Treatment Schedule

RT Planning Simulation	RT Treatment Day 1-5	RT Treatment Day 8-12	No. Fractions and Total Dose
Between Day -35 and Day -1	Week 1	Week 2	3 Gy per fraction per irradiated site for all participants
			To a total dose of 30 Gy in 10 fractions for each site
			Uniform dose prescription in all participants and uniform dose to all PTVs throughout the RT course

PTV=planning target volume, RT=radiotherapy.

Dose Calculations

All radiation doses will be calculated with inhomogeneity corrections that take into account the density differences within the irradiated volume.

Technical Factors

Beam Energy

Six- to 18-MV photons are recommended for non-superficial tumor targets; however, beam energy and type will be left to the discretion of the treating radiation oncologist in order to obtain the best dose distribution for the site being treated.

Beam Shaping

Multileaf collimation (MLC) or individually shaped custom blocks should be used to protect normal tissues outside of the target volume.

Localization, Simulation, and Immobilization

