Racc(AUC0-12) Accumulation ratio for AUC0-12 calculated as AUC0-12,D15/AUC0-12,D1 (Part A only).

Frel(AUC0-6) Relative bioavailability for AUC0-6 of fed (D22) compared to fasted (D15)

AUC0-6,fed/ AUC0-6,fasted and as sensitivity analysis AUC0-6 of fed (D1) compared to

fasted (D15) AUC0-6,fed/ AUC0-6,fasted (Part FE only).

λz Terminal first order elimination rate constant.

t½ Apparent terminal half-life,  $t_{\frac{1}{2}} = \ln 2/\lambda_z$ .

The following PK parameters will be reported for M3814 on Day 1 (FD1) and Day 12 (FD10) in Part B where data permit. Concentration results collected on Day 2 (FD2), Day 8 (FD6), and EoT will be summarized descriptively.

Cmax Maximum observed concentration

Cmax/Dose The dose-normalized maximum observed concentration. Normalized using the

actual dose, and the formula Cmax/Dose.

Ctrough The concentration observed immediately before next dosing on FD10 only.

Ctrough/Dose The dose-normalized trough concentration. Normalized using the actual dose, and

the formula Ctrough/Dose on FD10 only.

AUC0-6 Area under the concentration-time curve (AUC) from time zero to time 6 hours

postdose. AUC0-6 will be based on the estimated concentration at 6 hours and not

the concentration at the actual observation time.

AUC0-6/Dose The dose-normalized AUC from time zero to 6 hours postdose. Normalized using

the actual dose, using the formula AUC0-6/Dose.

AUC0-24 Area under the concentration-time curve (AUC) from time zero to time 24 hours

postdose. AUC0-24,FD1 will be based on the estimated concentration at 24 hours after dosing and not the concentration at the actual observation time. AUC0-24,FD10 from zero to 24 hours postdose with predose FD10 concentration used for estimated

concentration at 24 hours.

[figure not shown]
AUC0-24/Dose The dose-normalized AUC from time zero to 24 hours postdose for FD1 and FD10.

Normalized using the actual dose, using the formula AUC0-24,FD1/Dose and

AUC0-24,FD10/Dose.

tmax Time to reach the maximum observed concentration Cmax

Racc(Cmax) Accumulation ratio for Cmax, calculated as Cmax, FD10/Cmax, FD1

The following PK parameters will be reported for avelumab where data permit.

CEOI Concentration observed at the end of infusion period.

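### Part B treats the FD10 predose sample as a 24 h concentration with no check on the interval; for a Tuesday start it is a 72 h value, and the same note at FD6 is wrong on the printed calendar

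*Protocol*

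**What the plan says.** Protocol Table 6 (section 1.3) attaches the same rule to the predose samples at FD2, FD6 (Day 8) and FD10 (Day 12): "For M3814 PK parameter calculations, the predose value will serve as an estimate for the 24 h postdose concentrations of the previous fraction day". Its only calendar exception moves sampling to FD9 when Day 12 (FD10) is a Friday.

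M3814 is given only on radiotherapy days. The footnote to Protocol Table 14 states that "M3814 will be administered once a day for 5 days followed by 2 days off for 10 days in total". Appendix 8 prints the second week as "RT Treatment Day 8-12". It also spreads the 10 fractions over working days, with Saturday and Sunday generally off, and adds: "The participant can initiate treatment any day of the week".

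SAP 16.1 reports Part B M3814 parameters for FD1 and FD10 only:

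- AUC0-24,FD10 runs "from zero to 24 hours postdose with predose FD10 concentration used for estimated" concentration at 24 h.
- Ctrough and its dose-normalized version are taken at FD10.
- AUC0-24,FD1 uses an estimated 24 h concentration.
- FD2 and FD6 concentrations are only summarized descriptively.

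**The concern.** A predose sample stands in for the 24 h concentration only if the previous dose was given about 24 h earlier. With no weekend dosing, the first predose sample after a weekend comes 72 h after the last dose. If such a value is entered at 24 h, the AUC over the dosing interval is too low for a reason unrelated to dose, and so is a Ctrough read from it. Part B cohorts have 3 to 6 participants, so one affected profile is visible in a dose-level summary.

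**Working it through.** **Step 1. The plan's own figure.** The stated interval is 24 h. On the printed calendar (Days 1-5 and 8-12):

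- FD2: Day 2 − Day 1 = 1 day = 24 h. Reproduced.
- FD6: Day 8 − Day 5 = 3 days = 72 h. Not reproduced.
- FD10: Day 12 − Day 11 = 1 day = 24 h. Reproduced. The FD9 substitute (Day 11 − Day 10) is also 24 h.

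**Step 2. Other start days.** Inputs are the working-day rule and the free start day in Appendix 8. Interval = 24 h × (day of FDn − day of FDn−1), ignoring the predose window of up to 1 h.

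| Start | FD2 | FD6 | FD10 |
|---|---|---|---|
| Monday | 24 h | 72 h | 24 h (Day 12 is a Friday, so FD9 is sampled: 24 h) |
| Tuesday | 24 h | 24 h | 72 h (FD9 Friday Day 11, FD10 Monday Day 14) |
| Wednesday | 24 h | 24 h | 24 h |
| Thursday | 24 h | 24 h | 24 h |
| Friday | 72 h | 24 h | 24 h |

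**Step 3. Which 72 h values reach a reported parameter.**

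- FD6, Monday start: none. No FD5 parameter is calculated. The descriptive FD6 summary mixes 72 h and 24 h values if start weekdays vary.
- FD2, Friday start: none. AUC0-24,FD1 uses an estimated 24 h concentration.
- FD10, Tuesday start: AUC0-24,FD10, Ctrough and their dose-normalized versions.

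**Step 4. Size at FD10.** The documents give no half-life, so this is illustrative. Assume mono-exponential decline from 100 units at 2 h, C(t) = 100 × 2^(−(t−2)/t½), with samples at 0, 2, 4 and 6 h plus the assigned 24 h point. AUC is linear when rising and logarithmic when falling. The time-zero value is the observed predose value in both columns, so only the 24 h point differs. For the last segment, area = 18 × (C6 − Cend)/ln(C6/Cend).

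Example, t½ = 4 h: C6 = 50, C24 = 2.21, C72 = 0.00054.

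- Area 0-6 h = 388.5.
- Last segment with C24: 18 × 47.79/3.119 = 275.8, total 664.3.
- Last segment with C72: 18 × 50.00/11.44 = 78.7, total 467.2.
- Change: 467.2/664.3 − 1 = −29.7%.

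| Assumed t½ | C24/C72 = 2^(48/t½) | AUC0-24 with C24 | with C72 | Change |
|---|---|---|---|---|
| 4 h | 4096 | 664.3 | 467.2 | −29.7% |
| 6 h | 256 | 897.5 | 569.0 | −36.6% |
| 8 h | 64 | 1082.8 | 660.1 | −39.0% |
| 12 h | 16 | 1347.2 | 825.4 | −38.7% |

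If the comparison profile also takes C24 as its time-zero value, the changes run from −29.9% to −39.9%. At t½ = 24 h the ratio is 4 and the change −30.7%.

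If profiles are otherwise alike, one affected participant lowers a cohort mean by 30-40% divided by n: about 10-13% with n = 3 and 5-7% with n = 6.

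**Step 5. Whether existing rules catch it.**

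- The FD9 exception applies only when Day 12 is FD10 and a Friday, which under the working-day rule means Monday starts.
- The predose window is measured back from the next dose, so a 72 h sample is within window.
- Noncompartmental analysis uses actual elapsed times, but the FD10 predose value is placed at 24 h by definition.
- Values below the limit of quantification (BLQ) at the end of the 24 h interval are left out of AUC0-24. This covers a BLQ 72 h value, but not a low quantifiable one. It does not cover Ctrough either, because the SAP otherwise sets BLQ values to zero.

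**The case against.** The strongest objection is about reach. A reader of Table 6 might infer that weekend gaps at FD2, FD6 and FD10 all distort Part B exposure. The SAP does not support that: FD2 and FD6 values enter no reported parameter, and FD10 is affected for one start weekday out of five.

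The second objection is that the documents contain two calendars. If the five days on and two off are counted from Day 1 whatever the weekday, FD10 is always 24 h after FD9 and FD6 is always 72 h after FD5. There is then no FD10 bias and no mixing at FD6. This stands as a limit: the FD10 case depends on the Appendix 8 working-day rule. It does not remove the point, because Appendix 8 expressly allows any start day, and counting from Day 1 after a Tuesday start would put a fraction on a Saturday. The FD6 note is wrong on the printed calendar in any case.

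Third, the size depends on an assumed half-life. At short half-lives, where the concentration ratios are largest, the 72 h value is also the most likely to be BLQ and so excluded from AUC0-24. No quantification limit is given, so this cannot be settled.

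Fourth, Part B pharmacokinetics are secondary and descriptive. The SAP plans no AUC accumulation ratio for Part B, and Cmax and AUC0-6 do not use the substitution. A reader might infer that dose-escalation decisions are compromised. The documents do not show that: escalation rests on DLTs and adverse events, with available PK data as a further consideration.

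**Conclusion.** The point holds in a narrow form. The 24 h note is wrong for FD6 on the printed calendar, with a descriptive consequence only. For a Tuesday start on the working-day schedule, following SAP 16.1 as written puts a 72 h concentration at 24 h in AUC0-24,FD10 and reports it as Ctrough. If the value is quantifiable, that participant's AUC0-24,FD10 is roughly 30-40% too low for assumed half-lives of 4-12 h, and Ctrough is lower than a true 24 h value by a factor of 16 to about 4100. If the value is BLQ, the AUC is already protected. The number of participants affected depends on how many start on a Tuesday, which the documents do not indicate. It should be corrected because a stated rule gives a wrong reported parameter and the remedy is cheap. It does not show a general bias in Part B exposure.

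**What to change.** - **Protocol Table 6:** delete the 24 h note from the FD6 row. At FD2 and FD10, limit it to cases where M3814 was given on the previous calendar day.
- **SAP 16.1:** use a predose value as the 24 h concentration or as Ctrough only when about 24 h, within a stated window, have passed since the previous dose. Otherwise flag the value and use the estimated 24 h concentration, as already planned for FD1, where the terminal rate constant can be estimated. Where it cannot, report AUC0-6 only.
- **FD6 summary:** present predose concentrations by actual hours since the last dose.
- **Calendar:** reconcile the printed Days 1-5 and 8-12 with the Appendix 8 statement that treatment may start on any day of the week.

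The cost is one table note, a short SAP condition and a calendar clarification, with no added samples or visits. The downside is that a few participants may have no FD10 AUC0-24 or Ctrough.

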2.1 Study Rationale

This study is part of a clinical development program which aims to evaluate the clinical utility of M3814, a DNA damage target agent, with avelumab, an anti-PD-L1 therapy, with and without RT in a broad range of cancers.

In addition, the food effect (FE) on PK of M3814 will be investigated to evaluate the effects of prandial state and fat content of meals on the pharmacokinetic (PK) parameters of M3814.

The first part of this study (Part A) will assess M3814 in combination with avelumab in participants with advanced or metastatic solid tumors for which no standard therapy exists, standard therapy has failed, or participants are intolerant to or have rejected established therapy known to provide clinical benefit for their condition.

The second part of this study (Part B) will assess M3814 in combination with avelumab and RT in participants with advanced or metastatic solid tumors for which no standard therapy exists, standard therapy has failed, or participants are intolerant to or have rejected established therapy known to provide clinical benefit for their condition and are amenable to receive RT.

The third part of this study (Part FE) will assess the FE on PK of M3814 when administered in combination with avelumab under fasted and fed conditions in participants with advanced or metastatic solid tumors for which no standard therapy exists, standard therapy has failed, or participants are intolerant to or have rejected established therapy known to provide clinical benefit for their condition. Only doses of M3814 already declared safe and tolerable in Part A by the Safety Monitoring Committee (SMC) will be introduced in this part of the study.

2.1.1 Combining a DNA Damage Agent with M3814, a DNA Repair-Targeted Therapy

M3814 is a DNA-PK inhibitor which targets tumor cell growth and survival by inhibiting a critical double-strand break (DSB) DNA damage repair (DDR) mechanism. The antitumor effect of M3814 is dependent on the functionality of DNA repair and checkpoint signaling in cancer cells, which have a lowered ability to cope with DSBs, leading to cell death. Hence, the rationale of DNA-PK inhibition is to increase the amount of DSB DNA damage generated by DNA-damaging agents including direct DNA-damaging chemotherapy agents or Ionizing Radiation (IR).

In combination with etoposide and cisplatin in the NCI-H526 xenograft model, M3814 showed a better tumor control compared to etoposide + cisplatin or M3814 alone.

2.1.2 Combining Radiation, a DNA Damage Agent with M3814, a DNA Repair-Targeted Therapy and Immunotherapy

In addition to the potential of using DDR inhibitors in combination regimens with other DDR inhibitors or with DDR damaging agents such as standard-of-care chemotherapy or RT treatments, it is increasingly recognized that some consideration might be given to identifying optimized approaches to using DDR inhibitors alongside immunotherapy agents including immune checkpoint inhibitors. While many mechanisms by which DDR damaging agents can elicit antitumor immunity have been identified, the mechanisms by which DNA repair-directed agents (such as ATM, ATR, or DNA-PK catalytic subunit [DNA-PKcs] inhibitors) modulate the tumor immune environment and affect sensitivity to immune checkpoint inhibitors still need to be fully elucidated. However, it is reasonable to hypothesize that genomic instability induced by disruption of normal DNA repair pathway function could result in increased tumor mutational burden, neoantigens, and/or STING pathway activation, all of which could contribute to heightened immune checkpoint inhibitors sensitivity (McGranahan 2016; Mouw 2017).

Teo 2018 reported in subjects with metastatic urothelial cancer and treated with anti-PD-1/anti-PD-L1 antibodies atezolizumab and nivolumab, that the presence of DDR alterations was strongly associated with a higher objective response rate than those without any DDR alterations (67.9% versus 18.8%; p < 0.001). The median overall survival (OS) was not reached for subjects with deleterious DDR alterations, with 71.5% alive at 12 months, whereas the median OS for those with DDR alterations of unknown significance or no detectable DDR alterations were 23.0 and 9.3 months, respectively.

Several clinical studies are now under way to test the safety and efficacy of combinations of DNA repair-targeted agents with immune checkpoint inhibitors in both DNA repair-deficient and DNA repair-proficient settings (Yap 2015).

The interaction between the immune system and IR has been appreciated for many decades. Therapeutic radiation creates numerous types of DNA damage, including DSBs and the immune system can impact radiation-associated tumor control both locally (within the radiation field) and distantly (at unirradiated tumor sites).

Radiation increases PD-L1 expression on tumor cells, and this inhibitory effect can be overcome with PD-L1/PD-1 blockade resulting in a better tumor control

and improvement of survival compared to each treatment regimen alone (Deng 2014; Dovedi 2014).

Another study showed that radiation, anti-cytotoxic T-lymphocyte-associated protein 4 (CTLA4), and anti-PD-1/PD-L1 agents function in nonredundant ways to activate the immune system. Data from melanoma patients CCI suggest that although radiation diversifies the T cell repertoire and anti-CTLA4 therapy inhibits regulatory T cells, anti-PD-L1 therapy is necessary to overcome resistance driven by increased PD-L1 expression on tumor cells (Twyman-Saint Victor 2015).

Furthermore, clinical case reports and retrospective analyses suggest that a treatment regimen combining immune checkpoint blockade treatment and RT in a variety of solid tumors may result in a better disease control and longer survival than that seen with immune checkpoint blockade treatment alone, with an acceptable safety profile (Hiniker 2016, Ahmed 2017, Olson 2015, Shaverdian 2017). Based on these findings, clinical studies combining radiation and immune checkpoint therapies are ongoing in a variety of tumors in different clinical settings.

Taken together, the emerging experimental and clinical evidence suggests that DNA lesions arising from different backgrounds (increased DNA damage exposure [i.e. RT as exogenous source of damage and/or decreased DNA repair capacity {DDR inhibitor agent}]) often leads to increased mutational load and neoantigen burden, both of which have been correlated with immune checkpoint blockade response in a variety of settings. Therefore, combining an immune checkpoint inhibitor such as a velumab with a DNA-damaging agent such as RT and a DNA repair-targeted agent such as a CCI may be a useful therapeutic strategy in patients suffering from cancer.

The purpose of this Phase I study is to evaluate the safety, tolerability, PK/Pd profile and preliminary clinical activity of M3814, in combination with avelumab with and without RT in participants with advanced or metastatic select solid tumors. Part A of the dose escalation will establish the maximum tolerated dose (MTD) and/or recommended Phase II dose (RP2D) of M3814 when administered in combination with avelumab, while Part B will define the MTD and/or RP2D of M3814 when administered in combination with avelumab and RT. In addition, the Part FE will assess FE on PK of M3814 when administered in combination with avelumab under fasted and fed conditions.

